RATIONALE	Our study will test the feasibility of providing whole blood (WB) for resuscitation of adult male trauma patients in hemorrhagic shock and determine the effects of WB on clinical outcomes as well as the effects on coagulation, fibrinolysis, and inflammation, and hemolytic transfusion reactions compared to standard blood component therapy.
STUDY DESIGN	Prospective cohort study
PRIMARY OBJECTIVE	1. Compare volume of blood transfusion within 24 hours of admission between patients receiving whole blood and standard component therapy.
SECONDARY OBJECTIVES	The study will also compare: 1. Functional coagulopathy as measured by thromboelastography;

	
 2. 30-day mortality; 3. Number of units of blood products transfused by component/product; 4. Complications; 5. Hemolysis; 6. Wastage of blood units.
NUMBER OF PATIENTS	
Whole blood arm - 49 male patients over apparent age 18. Component therapy arm –49 male and female patients over apparent age 18.

PATIENT SELECTION CRITERIA	
Inclusion Criteria:
 
 • Whole blood arm: Male trauma patients over apparent age 18 with massive transfusion activation and presenting systolic blood pressure <100, who are receiving or will receive whole blood for initial resuscitation • Component therapy arm: Male and female trauma patients over apparent age 18 with massive transfusion activation and presenting systolic blood pressure <100, who have received, are receiving or will receive component therapy for initial resuscitation. 
Exclusion Criteria:
 
 • Patients with burns over >20% total body surface area
TEST PRODUCT, DOSE, AND ROUTE OF ADMINISTRATION	
Group O+ whole blood stored at 1-6 °C for up to 10 days. Patients may receive up to 4 units during the initial phase of the proposed study, to be increased to up to 6 units (see 5.2 Safety Evaluations) Product is administered to replace ongoing blood loss and restore/maintain hemodynamic stability and hemostasis. Product will be transfused intravenously as needed during initial traumatic resuscitation only. Following administration of whole blood if further transfusion is needed during initial trauma resuscitation, or after resuscitation is completed, the patient will receive standard

PI: [name]

	component therapy (packed red blood cells, plasma and platelets in a 1:1:1 ratio).
CONTROL PRODUCT, DOSE AND ROUTE OF ADMINISTRATION	Component therapy consisting of packed red blood cells, thawed fresh frozen plasma and platelets in a 1:1:1 ratio. Product will be transfused intravenously as needed to replace ongoing blood loss and restore/maintain hemodynamic stability and hemostasis.
DURATION OF PATIENT PARTICIPATION AND DURATION OF STUDY	
Patient participation includes up to 24 hours of transfusion, up to 5 days of laboratory testing, and up to one year of follow up by chart review. Follow up by chart review will continue throughout the patient's hospital stay or up to one year, whichever is shorter. Most hospital stays are anticipated to be approximately 14 days.
 
Screening: not applicable
 
Treatment: 1 day / 24 hours. Patients will receive whole blood only during initial resuscitation for traumatic hemorrhage, which is generally complete within a few hours.
 
Follow-up: 5 days (laboratory testing) + chart review for up to 1 year if the patient remains in the hospital
 
The total duration of study enrollment and completion of follow up is expected to be two years.

CONCOMITANT MEDICATIONS	Allowed: all Prohibited: none

EFFICACY EVALUATIONS:
	

PRIMARY ENDPOINT
	
1. Primary analysis will compare volume of blood transfusion within 24 hours of admission for patients with traumatic hemorrhagic shock without severe TBI (GCS \leq8 and evidence of brain injury on imaging) who have received WB versus component therapy for initial resuscitation.


SECONDARY ENDPOINTS
	
 1. Volume of blood transfusion within 24 hours of admission for patients with severe TBI (GCS \leq8 and evidence of brain injury on imaging) and for entire cohort of patients. 2. Thromboelastography parameters including maximum amplitude, reaction time, alpha angle, fibrinolysis, and platelet function at 3 and 6 hours of resuscitation, after every 6 units of whole blood equivalent (WB or PRBCs), at the time of completion of resuscitation (time of last unit of blood product given), and on ICU days 1, 3 and 5. 3. 30-day mortality; 4. Duration of need for renal replacement therapy, mechanical ventilation, ICU admission, and hospital stay; 5. Number of units of blood products transfused by component/product during first 24 hours of admission and total for hospitalization; 6. Complications which include 30-day mortality, clinical coagulopathy, infection, venous thromboembolism, cerebrovascular accident, acute coronary syndrome, transfusion-related lung injury, transfusion-associated cardiac overload; 7. Hemolysis as measured by haptoglobin, bilirubin, lactate dehydrogenase, and direct antiglobulin 8. Wastage of blood units

SAFETY EVALUATIONS
	
Complications which include death, clinical coagulopathy, infection, venous thromboembolism, cerebrovascular accident, acute coronary syndrome, transfusion-related lung injury, transfusion-associated cardiac overload;
 
Hemolysis as measured by haptoglobin, bilirubin, lactate

	dehydrogenase, and direct antiglobulin.
PLANNED INTERIM ANALYSES	When approximately 50% of patients have been enrolled in the study, an interim analysis for safety will be conducted by the statistician and independent medical monitor. Serious adverse events will be monitored by the medical monitor on an ongoing basis throughout the study.
STATISTICS Primary Analysis Plan	For continuous variables including the primary endpoint (volume of blood products transfused during the first 24 hours of admission), the statistical method will depend on the distribution of the data. If the data appears to follow a normal distribution, a t-test will be used, otherwise, a nonparametric Wilcoxon rank sum test will be used. To analyze coagulopathy over time a mixed effects linear regression model will be used. A mixed effects linear regression model will also be used to adjust for confounding variables such as sex, age, comorbidities, severity of injury, and physiologic parameters of shock including pH and temperature, and use of a rapid transfuser (which more effectively warms blood).
Rationale for Number of Patients	A sample size of 49 whole blood group (study drug) and 49 component therapy group (control) patients (98 patients total) is estimated. 18 of these per group are expected to have severe TBI and will be excluded from primary analysis, leaving 31 patients per group for the primary analysis. Using a Type I error rate of 0.05, and effect size based on reduction of PRBC and plasma transfusions described in the sensitivity analysis in a study by Cotton et al, 31 patients per group is expected to have 80% power to detect a significant difference in volume of transfusion in 24 hours. ¹

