1.2 Overview of Clinical Studies

The change in standard practice from whole blood transfusion, to fractionation and component transfusion, occurred after the 1970s because of concerns over resource utilization and safety. However, there was no evidence documenting equivalence between whole blood and components for trauma patients, and new data is now suggesting that whole blood may be superior for obtaining hemostasis and oxygen delivery for the acutely bleeding trauma patient.²²

The first evidence that whole blood may be superior to component therapy for trauma patients comes from military studies in Iraq and Afghanistan using fresh whole blood (FWB). FWB was initially used as a source of platelets, in addition to PRBCs and

plasma, when platelets were not available in far-forward military settings.²³ A retrospective analysis of prospectively collected data from all transfused patients at 6 forward surgical teams comparing standard component therapy to component therapy with whole blood substituted for platelets found that when adjusted for confounding variables, patients who received FWB had a significant survival advantage.²³ Of note, a subgroup analysis of patients who received “universal-donor” group O FWB (49%) versus type-specific product found there was no difference in mortality between these groups, and that there were no transfusion reactions.

Similarly, a retrospective analysis of 354 combat casualties transfused at least one unit of PRBCs compared standard component therapy with PRBCs, plasma, and warm FWB.²⁴ Patients who received whole blood had significantly lower transfusion volume requirements, and received significantly less preservative and anticoagulant additive volume, compared to patients receiving standard component therapy. 24 hour and 30 day survival was significantly higher in the whole blood group.

On the civilian side, a recent randomized controlled pilot trial compared whole blood leukoreduced with a non-platelet-sparing filter and stored for up to 5 days at 1-6°C, supplemented with warm stored platelets, to regular component therapy in severely injured patients predicted to require large volume transfusion.¹ There was a trend towards decreased plasma and platelet requirements in the whole blood group in the on-protocol analysis. In post hoc analysis use of whole blood was associated with a reduction in the amount of transfusion when traumatic brain injury was excluded.

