15.1 Data Sets Analyzed

All eligible patients who are enrolled in the study and receive at least one unit of blood, and who undergo TEG testing as described above, will be included in analysis.

Data sets include:

PI: [name]

1. Prospectively identified patients who received whole blood or component therapy and did not have severe TBI
2. Prospectively identified patients who received whole blood or component therapy and who had severe TBI (GCS 8 or less with evidence of brain injury on imaging)
3. Prospectively identified patients who received whole blood or component therapy, all patients regardless of TBI status
4. Prospectively identified male patients who received whole blood and who did not have severe TBI, compared to historical control male patients who received component therapy and who did not have severe TBI

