15.5 Interim Analysis

When approximately 50% of patients have been enrolled in the study, an interim analysis for safety is planned to be conducted by the independent medical monitor. (See Section 5.2, Safety Evaluations).

Sample Size

Number of patients to be enrolled was calculated using a Type I error rate of 0.05, and effect size based on reduction of PRBC and plasma transfusions described in the sensitivity analysis in a study by Cotton et al. ¹

As in the sensitivity analysis by Cotton et al, patients with severe TBI (defined as TBI on imaging with GCS of 8 or less) will be excluded from primary analysis. Approximately 35-40% of patients meeting inclusion criteria are expected to fulfill criteria for severe TBI. It is not possible to identify patients with severe TBI prior to beginning resuscitation for hemorrhagic shock, so all patients meeting inclusion criteria will be enrolled. In the primary analysis, only patients without severe TBI will be compared. Secondary analyses will compare 1) patients with severe TBI receiving WB versus component therapy and 2) the entire cohort of enrolled patients, with and without TBI, receiving WB versus component therapy. Using this method, a total sample size of 49 whole blood arm (study drug) and 49 component therapy arm (control) patients (98 patients total) is planned. 35-40% (approximately 18 of the total 49) of eligible patients are expected to have severe TBI and to be excluded from primary analysis based on typical presentations of trauma patients. 49 total patients per group will achieve a sample size of approximately 31 patients per arm without TBI to complete the primary analysis. The FDA will be notified in advance if sample size estimates change.

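### Secondary endpoint 1 neither stratifies nor explicitly adjusts the entire-cohort comparison for severe TBI, and its separate TBI and non-TBI tests invite a contrast of p-values

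*Protocol*

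**What the plan says.** The primary analysis (Sections 5.1 and 15.3) compares 24-hour transfusion volume in patients without severe TBI. Secondary endpoint 1 (Synopsis and Section 5.1) adds "Volume of blood transfusion within 24 hours of admission for patients with severe TBI" and the same comparison in the whole cohort. Section 15.5, under Sample Size, repeats this: "Secondary analyses will compare 1) patients with severe TBI receiving WB versus component therapy and 2) the entire cohort of enrolled patients". The pooled data set in Section 15.1 is "Prospectively identified patients who received whole blood or component therapy, all patients regardless of TBI status".

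Section 15.3 assigns continuous variables a t-test or, if the data look non-normal, a Wilcoxon rank sum test. Section 15.4 extends this to secondary endpoints. The Synopsis and Section 15.4 also provide a mixed effects linear regression to "adjust for confounding variables such as sex, age, comorbidities, severity of injury, and physiologic parameters of shock including pH and temperature", and they add use of a rapid transfuser. Severe TBI and GCS are not named there. No TBI-stratified pooled estimate and no treatment-by-TBI term appears.

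The reason for separating TBI is in Section 1.2: in the civilian pilot trial, whole blood was "associated with a reduction in the amount of transfusion when traumatic brain injury was excluded". Section 8.1 says that treatment is not assigned; it follows the patient's sex and whether whole blood is in stock.

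**The concern.** Severe TBI is the variable on which the design turns. It decides who enters the primary analysis and raises enrolment from 31 to 49 per group. The protocol nevertheless pools patients with and without it in an unadjusted test, and its list of confounders reaches rapid transfuser use without naming it. Two things follow.

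- **Entire cohort.** With no randomisation, nothing in the design balances the TBI share between groups. If TBI affects volume and the shares differ, part of the observed difference belongs to TBI and not to whole blood.
- **Strata side by side.** The non-TBI and TBI comparisons differ in size by design. A significant result in the larger and a non-significant result in the smaller would look like confirmation of the pilot trial's post hoc pattern, even if the effect were the same in both.

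**Working it through.** **Inputs from the protocol**
- Synopsis: "Using a Type I error rate of 0.05, and effect size based on reduction of PRBC and plasma transfusions", and "31 patients per group is expected to have 80% power to detect a significant difference in volume of transfusion in 24 hours". Sidedness is not stated; two-sided is assumed.
- Effect size and SD: no numbers are given. Section 15.5 says only "effect size based on reduction of PRBC and plasma transfusions described in the sensitivity analysis".
- 49 enrolled per group; severe TBI in 35-40%, about 18 per group.

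**1. The plan's own figures.** 49 − 18 = 31 per group, so the exclusion step reproduces (18/49 = 36.7%; at 35% 31.9 remain, at 40% 29.4). The 80% power cannot be reproduced without an effect size, so it is solved backwards:
- t-test: 80% power at 31 v 31 needs d = 0.723 SD.
- Normal approximation: d = (1.960 + 0.842) × √(2/31) = 0.712 SD.
- Variants: 0.63 SD if one-sided, 0.74 SD for a Wilcoxon test with relative efficiency 0.955.

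**2. Separate stratum tests when the true effect is identical (d = 0.723, t-test)**

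| Stratum | n per group | Power |
|---|---|---|
| Without severe TBI | 31 | 80.0% |
| Severe TBI | 18 | 55.9% |

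- Significant without TBI, not significant with TBI: 0.800 × (1 − 0.559) = 0.353, about 35%.
- The reverse pattern: 0.200 × 0.559 = 0.112.
- Discordant in either direction: 0.353 + 0.112 = 0.465, about 46%.

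The normal approximation gives 57% power at 18 per group, and 34% and 46% for the first and last of these. Discordant p-values are therefore common with no difference in effect, and the likelier direction is the one that echoes the pilot trial.

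**3. What a direct comparison of the strata can deliver**
- SE of the difference in effects = √(2/31 + 2/18) = 0.419 SD.
- If the effect is 0.723 SD without TBI and zero with it: 0.723/0.419 = 1.73; power = Φ(1.73 − 1.96) ≈ 41% (40% with d = 0.712).
- Difference detectable with 80% power: (1.960 + 0.842) × 0.419 = 1.17 SD, about 1.65 times the implied primary effect of 0.712 SD.

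**4. Imbalance in the entire cohort.** Shift in the unadjusted mean difference = (difference in TBI share) × (effect of TBI on volume, in SD). Neither factor is in the documents, so these are assumed ranges.
- SE of the entire-cohort difference = √(2/49) = 0.202 SD.
- Chance variation in TBI share: √(2 × 0.367 × 0.633/49) = 0.097, so a 95% range of ±1.96 × 0.097 = ±19 percentage points.
- If a systematic imbalance b = share difference × TBI effect existed, the type I error would be 1 − Φ(1.96 − b/0.202) + Φ(−1.96 − b/0.202):

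| Assumed TBI effect | Assumed share difference | Shift | Share of 0.712 SD | Type I error |
|---|---|---|---|---|
| 0.25 SD | 10 points | 0.025 SD | 4% | 5.2% |
| 0.50 SD | 20 points | 0.10 SD | 14% | 7.9% |
| 1.00 SD | 30 points | 0.30 SD | 42% | 32% |

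The width of this range shows that the size of any bias cannot be settled from the protocol.

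**The case against.** The strongest reply has five parts.

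- **This is SAP detail.** Section 15 promises a detailed SAP, and interaction terms and the final covariate set are often settled there. That is fair for a topic on which the protocol is silent. Here it fixes the comparisons and the tests and lists confounders, so the stated method can be judged as it stands.
- **The covariate list is illustrative.** It is introduced as examples and includes severity of injury, and Section 10.1 collects GCS and Injury Severity Score. This stands. A reader might infer that the entire-cohort result carries any TBI imbalance in full; the documents support that only for the unadjusted test. An overall severity measure need not isolate head injury, so the adjusted model may remove only part.
- **No claim of a different effect by TBI is made.** True: no objective or endpoint states one. A reader might also infer that the plan cannot show whether the effect differs by TBI. That goes too far: the strata contain different patients, so the difference and its interval can be derived from the planned comparisons. The plan simply does not say that this will be done.
- **Chance imbalance is not bias.** Correct. The ±19 points is sampling variation already reflected in the standard error. Even at that limit with a 1.0 SD TBI effect, the shift of 0.19 SD is below one standard error (0.202 SD). Bias needs a systematic difference in TBI share. The protocol identifies no mechanism for one: product follows sex and stock, severe TBI cannot be recognised before resuscitation starts, and sex is a named covariate. What remains is that non-random allocation gives no assurance of balance.
- **The reach is small.** It is: one of eight secondary endpoints, with the primary analysis already restricted to patients without severe TBI.

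**Conclusion.** The concern holds as a minor to moderate improvement to secondary endpoint 1. The stated entire-cohort test ignores the one patient characteristic that the protocol itself uses to split its population, and in a non-randomised study it is exposed to any difference in TBI share. How large that effect would be is unknown, and the bias figures above are illustrations under assumed values.

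The firmer number is the roughly 35% chance that identical effects would give significance without TBI and none with it. It rests on a two-sided 5% t-test, the 31 and 18 per group in the plan, and an effect of 0.72 SD in both strata, back-solved from the stated 80% power. It shows that two stratum p-values would be a poor basis for saying the effect differs by TBI. It does not show that the protocol makes that inference.

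**What to change.** For secondary endpoint 1:

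1. Analyse the entire cohort with severe TBI as a covariate or stratum: a regression with treatment, severe TBI and the covariates already named, or a van Elteren test stratified by severe TBI if ranks are used because volume is not normal.
2. Report the difference in whole blood effect between patients with and without severe TBI, with its confidence interval, as exploratory (for example from a treatment-by-TBI term added to the regression).
3. State that no conclusion about a different effect by TBI will be drawn from comparing the stratum p-values.

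The cost is wording. TBI status is already needed to define the primary set, so no new data or patients are required. The limitation is precision: with about 41% power even if the effect disappears entirely in severe TBI, the interaction is an estimate with a wide interval, and a non-significant result must not be read as evidence of equal effects.

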1 BACKGROUND

Massive hemorrhage is a major cause of potentially preventable death following trauma.²⁻⁶ A common consequence of hemorrhagic shock is uncontrollable bleeding from coagulopathy, leading to death from exsanguination. Even when bleeding is controlled, patients are at increased risk of complications and mortality.^{7,8} Reconstituted whole blood, or component therapy with PRBCs, plasma, and platelets was introduced by the military in recent conflicts in Iraq and Afghanistan with remarkable results and has been adopted by most civilian trauma centers.⁹ Despite improving coagulopathy, it is apparent that transfusion of blood components is not equivalent to whole blood transfusion.¹⁰⁻¹² Transfusion of high plasma volumes may be associated with increased risk of allergic reaction, transfusion associated acute lung injury (TRALI), hypervolemic cardiac failure/transfusion-associated circulatory overload (TACO), and ARDS.¹³

Military services that have recently reintroduced fresh whole blood (FWB) for standard resuscitation of massive hemorrhage have found that FWB offers a survival advantage over component therapy, and that risks of transfusion reactions are similar for FWB and component therapy with PRBCs.⁶ On the civilian side, whole blood is an FDA-licensed product that has been in use in pediatric open heart surgery and autologous transfusion but is no longer commonly available for other indications. However, the military results are renewing interest in whole blood for trauma resuscitation. The use of low-titer (anti-A/anti-B) group O-positive whole blood that is leukoreduced with a platelet-sparing filter was recently approved by the UCLA Blood and Blood Derivatives Committee (Transfusion Committee) for male trauma patients.

To provide effective treatment for traumatic hemorrhage, blood product transfusion must provide the oxygen-carrying capacity provided by red blood cells and the hemostatic capacity provided by platelets and clotting factors. Whole blood offers the advantages of more precisely approximating shed blood; decreased volume of additives per transfusion episode; and exposure to a decreased number of donors for a patient undergoing massive transfusion. As described below, the military experience, initial civilian studies, and preclinical studies indicate that whole blood may be superior to component therapy particularly with regard to hemostatic capacity, though it remains to be seen whether this will translate into differences in coagulopathy, inflammation, transfusion requirements, and mortality. Additional considerations include optimal storage conditions that maintain the function of red cells, platelets, and clotting factors; as well as careful consideration and mitigation of the risk of transfusion reaction when the group O plasma in whole blood units is administered to non-group O recipients. Evidence of the safety of this product is provided in the following sections.

